**SYSTEMATIC INVESTIGATION OF BLACKS WITH STROKE- GENOMICS
(SIBS-GENOMICS) STUDY**

SEPTEMBER 5TH, 2022

PILOT TRIAL

Specific Aim. To determine the effectiveness of the Afrocentric stroke riskometer mobile phone application combined with the motivation stroke educational video and educational modules for improvement of individual awareness and reduction of the total quantitative risk of stroke through a randomized controlled trial among stroke-free adults in Nigeria and Ghana.

Study design: A feasibility pilot study involving stroke-free adults with at least 2 vascular risk factors for stroke assigned to an educational intervention for 2 months comprising of a stroke video and riskometer App aimed at improving stroke risk factor awareness and health seeking behavioural modification to control vascular risk (n=50) compared with a control group (n=50) who are offered one time counselling.

Study Sites: 3 sites across Nigeria and Ghana

Study Participants: Study participants will be CONSECUTIVELY selected from the existing pool of stroke-free controls in SIREN and SIBS Genomics studies across the 3 study sites (60 from Ibadan, 20 from Kumasi and 20 from Zaria). The vascular risk factor profile of these control participants has already been assessed. Stroke free status at enrollment will be reconfirmed using the locally validated version of the QVSFS.

Eligibility criteria: **Inclusion criteria:** (i) male or female (sex is a biologic variable of interest), (ii) age \geq 18 years, (iii) with at least 2 stroke risk factors based on the list of 11 topmost modifiable risk factors identified in the SIREN study (including hypertension, diabetes mellitus, dyslipidemia, smoking, overweight, physical inactivity, or unbalanced/poor diet). (iv) ownership or access to smartphone in consenting stroke-free adults. **Exclusion criteria:** prior history of vascular disease (e.g., stroke, transient ischemic attack, angina, myocardial infarction, peripheral vascular disease, and atrial fibrillation), or cognitive impairment; not comfortable reading and writing, depression or other psychiatric disorders (through personal declaration) likely to affect the interventions; participation in another RCT; other conditions rendering the individual unsuitable to participate in this research as judged by treating physicians,

Justification for Eligibility Criteria: Individuals with existing high modifiable risk are more likely to be motivated to engage in behavioral change activities more so than those without.

Recruitment: Research coordinators (RCs) will obtain informed consent, schedule baseline assessment & alert statistician of a new participant to be randomized via REDCap. Randomization will be performed within 24 hours & baseline assessments within one week at the respective SIREN facility/community. Baseline assessment will include screening of all participants for stroke risk factors by trained RCs. Risk factor screening will include measurement of blood pressure, blood glucose and lipid profile, psychosocial assessment for stress, dietary recall to assess salt intake and vegetable consumption, waist circumference and body mass index.

Intervention: The app will not be installed on the smartphones during the pilot study to limit potential future exposure contamination. RCs will complete baseline screening assessment with participants and capture a screenshot of the individual's current global stroke risk score as a percentage, which will then be given to the participant via their smartphone (i.e., **screenshot of the score produced by the app**). Participants will be shown their risk scores and the specific risk factors identified through the screening. They will be asked to visit their doctors /primary care clinicians to facilitate management their risk factors through therapeutic lifestyle changes or pharmacotherapy, for example antihypertensives for hypertension, statins for dyslipidemia, or oral hypoglycemics for diabetes. This will be part of health seeking behaviour the app should promote, which will be assessed as part of process measure. Participants will receive monthly reminders on compliance/adherence to any clinician prescribed treatment or lifestyle modifications, as applicable, and to follow-up with primary provider if they haven't already and especially if their risks include hypertension, diabetes, or dyslipidemia. Participants will be asked to show their current global stroke risk to their clinician/doctor. As part of process measure, we will assess clinician acceptability and readiness to use the app to monitor their patients overall progress with total risk factor control. The records will be stored on our server, such that if they lose the score risk, the RC will be able to provide another copy (paper or digital) so their clinicians will still be able to access risk scores when shown by participants. In

addition, participants will be encouraged to watch the stroke video at least once monthly that will be shared via their smartphone, although they will be asked not to share it with others to minimize exposure beyond enrolled intervention participants.

Control group will be screened at baseline and be informed about their risk factors. They will be encouraged to seek medical therapy for a doctor after assessment of their baseline risk factors, should they have hypertension, diabetes, or dyslipidemia, but this advice will not be reinforced by either exposed to the app or the stroke video. They will complete a post-study questionnaire to assess any contamination with the intervention.

Randomization: will be at individual level, per site as the app is meant to be developed at individual level eventually.

Concealment of allocation: Blinding of participants is not possible given the nature of the intervention. However, the adjudicator and the study statistician will not be aware of the allocation status of study participants during outcome data collection and analysis respectively. Outcome assessors will not be involved in delivering the intervention. To ensure blindness, trial participants will be told not to divulge details of their treatment to the assessors. The randomization scheme which will be used to allocate patients to groups will be developed & maintained by the lead study biostatistician. Randomization database will be independent & will not be accessible to outcome assessors or other personnel. Whereas the research coordinators (RCs) will be aware of the randomization assignment, they will not have any role in the delivery of the intervention or outcome adjudication.

Outcome measures:

1. **Feasibility measures:** Proportion approached, proportion refused, proportion ineligible (reasons for ineligibility), proportion enrolled, proportion completing follow-up, & proportion visiting their doctors will be compared between the two groups.
2. **Satisfaction and acceptability measures:** (i) autonomous self-regulation was assessed using the 15-item Treatment Self-regulation questionnaire,¹⁴ (ii) patient satisfaction using the telemedicine satisfaction and usefulness questionnaire, (iii) reported side effects of medications, (iv) hypertension and stroke knowledge using a 14 item questionnaire & (v) adherence measures to medications prescribed for primary prevention and lifestyle advice (physical activity, dietary patterns, alcohol and cigarette use); and participant preferences, insights, and challenges in using the app and efforts toward adopting behavioral change collected through and end of study key informant interview.
3. **Signal of Efficacy measures:** 1.) Change in total stroke risk score at month 2 calculated as difference between baseline score and month 2 score. 2) Change in stroke risk factor awareness score. 3) differences in number of encounters with healthcare provider during the period of the trial in those who have either hypertension, dyslipidemia or diabetes.

Statistical Analysis: For this pilot trial, our sample size focused on precision of estimates for a future study design rather than power of statistical tests. We will compare medians and means for continuous variables using either the Mann-Whitney's U-test or Student's t-test (paired) while categorical variables will be compared using the Chi-squared tests. A $p < 0.05$ was considered significant difference between the 2 groups. Unadjusted odds ratios were calculated for primary outcome measures.

Qualitative Interviews: We will conduct key informant interviews (KIs) with intervention participants to explore personal perspectives on acceptability of the app and video, including barriers and facilitators of its use, behavioral change efforts made to reduce stroke risk, and recommendations for revision and educational module content. Educational module content via a wireframe of app content will be shared with participants to ascertain their perceptions and recommendations for content refinement. Additionally, factors related to the social determinants of health (SDOH) will be included to better understand influence on lifestyle modification, stroke risk, and access to care and adoption of recommended health behaviors. Clinician KIs will be completed to explore their acceptance and readiness to use the app, input of current treatment practices, recommendations for educational module content, behavioral modification strategies, clinical team educational needs, and barriers and facilitators toward intervention implementation. Interviews will be audio-recorded, transcribed and translated to English when necessary, and thematically analyzed using inductive and deductive approaches.

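### Risk factors are re-measured after randomisation, as the protocol naturally reads, by coordinators who know the arm, so eligibility and the baseline risk score may not be fixed before allocation

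*Protocol*

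**What the plan says.** Under Eligibility criteria, participants must be adults "with at least 2 stroke risk factors based on the list of 11 topmost modifiable risk factors identified in the SIREN study". Study Participants draws them from the control pools of two earlier studies and states: "The vascular risk factor profile of these control participants has already been assessed". It gives no date or maximum age for that assessment. The one item it re-checks is different: "Stroke free status at enrollment will be reconfirmed using the locally validated version of the QVSFS".

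Recruitment then sets the order of steps. Coordinators "will obtain informed consent, schedule baseline assessment & alert statistician of a new participant to be randomized via REDCap". Next, "Randomization will be performed within 24 hours & baseline assessments within one week". The baseline visit is where current status is measured: "Risk factor screening will include measurement of blood pressure, blood glucose and lipid profile", followed by stress, dietary recall, waist and body mass index. Trained coordinators do this for all participants.

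Concealment of allocation says that coordinators know the assignment, that participants cannot be blinded, and that outcome adjudication is blinded.

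Under Outcome measures, efficacy measure 1 is the change in total stroke risk score from baseline to month 2. Measure 2 is "Change in stroke risk factor awareness score". Measure 3 is "differences in number of encounters with healthcare provider during the period of the trial in those who have either hypertension, dyslipidemia or diabetes".

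**The concern.** A criterion that defines the trial population should be settled before allocation, and so should any baseline value that enters an outcome. Here the only current measurement of risk factors appears to come after allocation, and the protocol has no rule for a participant who then turns out to have fewer than two.

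Three things are at stake:

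- **Population.** The protocol justifies the criterion by saying that people who already carry modifiable risk are more motivated to change. Blood pressure, weight, diet and smoking can change over time, so an undated profile does not establish that risk at entry.
- **Efficacy measure 1.** Its baseline half can be collected by staff who know the arm, from participants who may know it too.
- **Efficacy measure 3.** A subset defined by information gathered after allocation by unblinded staff is not protected by randomisation. The protocol does not say which information defines it.

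**Working it through.** The protocol states no figure on this point to reproduce. The planned total is consistent: 60 + 20 + 20 = 100 by site and 50 + 50 = 100 by arm. The check is mainly one of sequence.

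**Order of steps**

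| Step | Timing | Content | Section |
|---|---|---|---|
| Earlier cohort assessment | Before the trial, undated | Risk-factor profile | Study Participants |
| Enrolment | Day 0 | Consent; stroke-free status re-checked; statistician alerted | Study Participants; Recruitment |
| Randomisation | Within 24 hours | Allocation, known to coordinators | Recruitment; Concealment of allocation |
| Baseline visit | Within one week | Blood pressure, glucose, lipids, stress, diet, waist, body mass index | Recruitment |

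The alert that triggers randomisation goes out when the baseline visit is scheduled, and nothing makes it wait for the visit to be completed. The Intervention section points the same way. The coordinator completes baseline screening and captures the app's risk score, which then goes to the intervention participant. This arm-specific step fits a visit at which the arm is already known.

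**Eligibility.** The two-risk-factor criterion is not re-checked at any step before randomisation. The share of the pool that no longer meets it is not given. Purely for scale, assume a rate p that is independent between participants. The expected number among 100 is 100p, and the chance of at least one is 1 − (1 − p)^100:

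- p = 2%: 2 expected; 1 − 0.98^100 = 0.867
- p = 5%: 5 expected; 1 − 0.95^100 = 0.994
- p = 10%: 10 expected; above 0.999
- p = 20%: 20 expected; above 0.999

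Even a low rate would probably produce at least one such participant. The rates are assumptions and not evidence from the protocol.

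**Efficacy measure 1.** Let B be the mean baseline score and M the mean month 2 score. The between-arm difference in change is

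D = (B_int − M_int) − (B_con − M_con).

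If knowledge of the arm shifts the intervention baseline by d relative to control, B_int becomes B_int + d, and D becomes D + d. The shift enters in full. Blinded assessment at month 2 does not cancel it, because that blinding protects M and not B. The protocol does not list the inputs to the score. The screening behind it includes dietary recall and a stress assessment, which are more open to such influence than blood pressure, glucose or lipids.

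**Efficacy measure 3.** Two sources could define the subset: the earlier cohort profile, which predates allocation, or the baseline screening. The Intervention section ties these three conditions to the baseline assessment when it describes the advice given to controls. That makes the screening a plausible source but does not establish it.

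**The case against.** The strongest defence is that eligibility may be meant to rest on the earlier profile. Those data predate allocation and apply equally to both arms. On that reading, a participant whose status has since changed was not randomised in error. This stands as far as the word error goes. It does not answer the lack of a date or a current check, and it does not touch the baseline risk score. Ineligibility is also a listed feasibility outcome, so some check is intended, but its timing is not given.

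A reader might infer several stronger claims that the protocol does not support:

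- *Risk factors are certainly measured only after allocation.* Both time limits are upper bounds, and a baseline visit before allocation is not strictly excluded. Post-allocation measurement is the natural reading, and nothing in the text prevents it.
- *The measure 3 subset is set by unblinded screening.* The source is not stated. Blood pressure, glucose and lipids are also objective, which limits the scope for biased classification.
- *Change in awareness cannot be computed, or smoking and physical activity go unmeasured.* The list says what screening will include and is not stated to be complete. A change score implies a baseline value. Both arms are told their risk factors, so that disclosure alone is not the contrast between arms.
- *Precision is lost through exclusions.* The protocol plans no exclusions after randomisation, and analysis sets may be defined in a statistical analysis plan that is not shown. No loss of precision is claimed here.

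**Conclusion.** The point holds in a limited form. As naturally read, the protocol allows the two-risk-factor criterion and the baseline total risk score to be assessed after allocation by staff who know the arm. It also leaves open whether the measure 3 subset is set in the same way. This is a weakness in the order of visits, and a later analysis plan cannot recover a pre-randomisation baseline that was never collected.

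The sequence applies to all 100 participants. The number without two current risk factors and the size of any shift in the baseline score cannot be derived from the documents. The conclusion rests on two readings: that the baseline visit usually follows the 24-hour randomisation, and that the baseline score comes from that visit. The change should be made because it is cheap and removes an avoidable route to bias. The protocol does not show that bias will occur.

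**What to change.** Reorder Recruitment so that the planned baseline screening is completed before randomisation. Then:

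1. Confirm the two-risk-factor criterion on that screening.
2. At the same visit, record the baseline awareness score before any risk score or risk factor is disclosed. This is a safeguard, since the protocol does not state the order.
3. Lock the baseline risk score in REDCap before allocation is released, with a yes/no flag for hypertension, dyslipidaemia or diabetes.
4. Name that flag as the denominator for efficacy measure 3.
5. Analyse everyone randomised, with no later removal on eligibility grounds.

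The visit and staff are already planned. Randomisation moves back by up to about a week, and a few people will be screened but not randomised. Those screen failures would feed the ineligibility proportion already listed among the feasibility measures.

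### The recruitment schedule lets research coordinators who know the allocation measure the baseline risk score after randomisation, and that score is one term of the change outcome

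*Protocol*

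**What the plan says.** **Order of events (Recruitment).** The coordinators' first step is: "Research coordinators (RCs) will obtain informed consent, schedule baseline assessment & alert statistician of a new participant to be randomized via REDCap". The timing follows: "Randomization will be performed within 24 hours & baseline assessments within one week at the respective SIREN facility/community". No sentence says which of the two comes first.

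**Who takes the baseline (Recruitment, Intervention).** "Baseline assessment will include screening of all participants for stroke risk factors by trained RCs". The screening covers blood pressure, glucose, lipids, waist and body mass index, together with a stress assessment and a dietary recall. Under Intervention, the coordinators complete this screening and capture the app's risk score from it.

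**Who is masked (Concealment of allocation).** The protocol says "the adjudicator and the study statistician will not be aware of the allocation status of study participants during outcome data collection and analysis respectively", and it keeps outcome assessors separate from delivery. Of participants it says: "Blinding of participants is not possible given the nature of the intervention". It closes the allocation list ("Randomization database will be independent & will not be accessible to outcome assessors or other personnel"), but its later sentence on the coordinators reads: "Whereas the research coordinators (RCs) will be aware of the randomization assignment, they will not have any role in the delivery of the intervention". It does not say when they learn the assignment.

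**What the baseline is used for (Outcome measures, item 3).** The first efficacy-signal measure is: "Change in total stroke risk score at month 2 calculated as difference between baseline score and month 2 score".

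**The concern.** A baseline used in a change score should be fixed before anyone involved in measuring it can know the arm. Here the schedule allows allocation on day 1 and baseline as late as day 7, taken by staff who are stated to know the allocation. Some of the screened items depend on what the participant reports (stress, diet), and blood pressure depends partly on the operator.

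If such items shift differently by arm, the total score may shift too, and the error goes straight into the difference in change. Masked assessment at month 2 cannot undo it, because the error lies in the other term.

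The Statistical Analysis paragraph justifies the sample size by how precisely quantities needed for a later trial can be estimated. An estimate of effect biased in this way would be a poor input if that later design uses it. The feasibility, acceptability and interview results are largely unaffected.

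**Working it through.** **Reading the schedule.** The protocol states no figure to reproduce here, so the first check is of the text.

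1. At the alert to the statistician, baseline has been booked, not done.
2. Randomisation has a limit of 24 hours and baseline a limit of one week. Both are ceilings. A baseline on day 0 would comply, and so would one several days after allocation.
3. Closing the randomisation database does not settle the matter, since the protocol goes on to say that the coordinators know the assignment. Nothing withholds it from them until baseline is complete.
4. The risk profiles already held from the parent studies do not settle it either. Recruitment and Intervention describe a new screening that yields the current score.
5. The finding is firm only for the risk score. The protocol does not say who takes the baseline awareness score, or when.

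**Size, as an illustration.** From the protocol: 50 per arm and a 0.05 significance level (taken as two-sided). Assumed: no true effect, scores with SD 1, correlation ρ between baseline and month 2, a net shift *d* in the measured total baseline score in one arm, and an unpaired comparison of change.

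- Change score: the bias equals *d*; SE = √[2(2 − 2ρ)/50]; 98 degrees of freedom.
- At ρ = 0.6: SE = √[2 × 0.8/50] = √0.032 = 0.179 SD, and the 95% half-width is 0.355 SD.
- Baseline-adjusted analysis (ANCOVA): the bias is ρ*d* in size; SE = √[2(1 − ρ²)/50]; 97 degrees of freedom. At ρ = 0.6: SE = √[2 × 0.64/50] = √0.0256 = 0.160 SD.

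Coverage is 1 minus the rejection rate from the noncentral t distribution:

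| Analysis | ρ | SE | Half-width | *d* = 0.05 | *d* = 0.1 | *d* = 0.2 |
|---|---|---|---|---|---|---|
| Change | 0.5 | 0.200 | 0.397 | 0.943 | 0.921 | 0.832 |
| Change | 0.6 | 0.179 | 0.355 | 0.941 | 0.914 | 0.802 |
| Change | 0.7 | 0.155 | 0.307 | 0.938 | 0.902 | 0.752 |
| ANCOVA | 0.6 | 0.160 | – | 0.946 | 0.934 | 0.885 |

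The ANCOVA biases at ρ = 0.6 are 0.6 × 0.05 = 0.03, 0.6 × 0.1 = 0.06 and 0.6 × 0.2 = 0.12 SD: reduced, not removed.

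A simulation at ρ = 0.6 (10,000 trials per cell) agrees. For *d* = 0, 0.05, 0.1 and 0.2, the t-test on change rejects in 0.048, 0.058, 0.085 and 0.199 of trials, and the Mann-Whitney test in 0.049, 0.058, 0.086 and 0.195.

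**How large a shift is plausible.** The protocol does not say which screened items enter the score, or with what weight. If the items open to influence carry an assumed share *w* of the standardised weight, the shift needed in those items is *d*/*w*:

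| *w* | *d* = 0.05 | *d* = 0.1 | *d* = 0.2 |
|---|---|---|---|
| 0.25 | 0.2 SD | 0.4 SD | 0.8 SD |
| 0.5 | 0.1 SD | 0.2 SD | 0.4 SD |

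The larger total shifts need large item shifts, so the smaller values of *d* are the more plausible.

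**The case against.** The strongest reply is that the harm needs several things the protocol does not state: that baseline does follow allocation, and that the coordinators (or participants) already know the arm at that visit. On this view the text shows only that the order and the release of the allocation are left open. That is right, and the claim goes no further than that; but leaving them open is the defect.

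The participant side is the weaker part. Participants are said to be unblindable because of what the intervention is, and the score is handed over after screening. No sentence says they learn their arm before the visit. It remains a possibility only; the case rests mainly on the coordinators.

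Most listed items are instrument or laboratory measures, the app computes the score, and no direction of bias can be named. This stands. It limits the likely size, as the dilution figures show.

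A comparison of month-2 scores alone would avoid the measured baseline altogether, with SE √(2/50) = 0.200 SD against 0.179 SD for change at ρ = 0.6. That is true, but it is not the outcome the protocol defines.

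Finally, this is a pilot, and the protocol does not say that the observed difference will size the next trial; variability or feasibility rates might serve instead. This stands too, and confines the consequence to the efficacy-signal estimates.

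**Conclusion.** The point holds. As written, the protocol allows an unmasked, post-allocation measurement to become one of the two terms of its first efficacy-signal measure, and no masking provision covers that measurement.

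Whether bias would occur, its direction and its size cannot be known from the document. Only the 50 per arm and the 0.05 level are documented; the correlation, shift and item weights are assumptions. Across assumed correlations of 0.5 to 0.7, coverage of a nominal 95% interval stays at about 94% for a 0.05 SD shift, is 92% to 90% for 0.1 SD, and 83% to 75% for 0.2 SD.

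This should be fixed because the gap is avoidable at little cost and an analysis can only reduce the error once the baseline has been collected, not because a large bias is expected. Self-report after the intervention stays open to bias even with the fix.

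**What to change.** State one of two orders in Recruitment.

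- **A.** Consent; complete and save the baseline risk score and awareness score in REDCap; then request randomisation, with the 24-hour limit running from that point.
- **B.** Keep randomisation within 24 hours of consent, but withhold the allocation from coordinators and participants until the baseline is saved.

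Either closes the gap. A also ensures that nobody is randomised without a baseline. B keeps the present timing but can leave a randomised participant with no baseline, and it needs a controlled release step in REDCap.

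Neither needs new measurements. The cost is a delay of up to about a week before allocation (A) or its release (B), and possibly one further contact to hand over the score and materials.

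Separately, and not as support for the above: Concealment of allocation says the coordinators have no part in delivery, while Intervention has them capture the score screenshot given to participants and supply replacement copies. These two paragraphs must be reconciled.

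### The risk and awareness scores are analysed as raw change with no baseline term, and the t-test named for comparing the two arms is labelled paired

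*Protocol*

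**What the plan says.** Under Outcome measures (Signal of Efficacy), the first measure is "Change in total stroke risk score at month 2 calculated as difference between baseline score and month 2 score" and the second is "Change in stroke risk factor awareness score". Both are raw differences from baseline.

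Under Statistical Analysis, continuous variables are to be compared "using either the Mann-Whitney's U-test or Student's t-test (paired"). The next sentence treats p < 0.05 as a difference between the two groups. No covariate is named. The same section says that "our sample size focused on precision of estimates for a future study design rather than power of statistical tests".

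Three other statements bear on the point:

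- Randomization: allocation "will be at individual level, per site", with 50 people per arm and 60, 20 and 20 people from the three sites.
- Recruitment: "Randomization will be performed within 24 hours & baseline assessments within one week".
- Intervention and Concealment of allocation: "RCs will complete baseline screening assessment with participants", and the "research coordinators (RCs) will be aware of the randomization assignment".

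**The concern.** There are two linked problems, plus a condition on which both the planned and the proposed analysis depend.

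**The paired label.** People are randomised individually and not matched, so the only pairs available are each person's own two scores. A paired t-test on those asks whether one arm changed. Both arms are screened, told their risk factors and encouraged to seek care, so some change common to both arms is plausible. A within-arm test would pick that up whether or not the app and video add anything.

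**No baseline term.** An unpaired comparison of change is a legitimate analysis, but it gives the baseline score a fixed coefficient of one. Estimating that coefficient is at least as precise in large samples. Any chance imbalance in baseline between the arms is part of this same loss of precision, not a further harm. The loss matters here because precision is the protocol's stated reason for the sample size.

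**The condition.** Both analyses are unbiased only if the baseline score cannot be affected by knowledge of the arm. The stated time limits allow baseline to follow randomisation, and the staff who take it know the assignment.

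**Working it through.** The protocol gives no SD, correlation, effect size or target interval width, so there is no figure of its own to reproduce. The counts agree: 60 + 20 + 20 = 100 = 50 + 50.

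**Inputs.** From the protocol: n = 50 per arm, individual 1:1 allocation within site, baseline and month-2 scores. Assumed: complete follow-up, two-sided 5% level, correlation ρ between baseline and month-2 scores, and month-2 SD equal to k times the baseline SD. Results are in units of the baseline SD.

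**Formulas.** The per-person variance is

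- change score: 1 + k² − 2kρ, which is 2(1 − ρ) when k = 1;
- baseline-adjusted: k²(1 − ρ²), which is 1 − ρ² when k = 1.

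The standard error of the arm difference is √(2 × variance / 50). With k = 1, the variance ratio (adjusted to change) is (1 − ρ²) / [2(1 − ρ)] = (1 + ρ)/2.

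**Equal SDs (k = 1).**

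| ρ | SE, change | SE, adjusted | Variance ratio | SE lower by | 95% half-width, change | 95% half-width, adjusted | Worth, of 100 participants |
|---|---|---|---|---|---|---|---|
| 0.5 | 0.200 | 0.173 | 0.75 | 13.4% | 0.397 | 0.345 | 25 |
| 0.7 | 0.155 | 0.143 | 0.85 | 7.8% | 0.307 | 0.284 | 15 |
| 0.8 | 0.126 | 0.120 | 0.90 | 5.1% | 0.251 | 0.239 | 10 |
| 0.9 | 0.089 | 0.087 | 0.95 | 2.5% | 0.177 | 0.174 | 5 |

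The change half-widths use t on 98 degrees of freedom. The adjusted ones are means over simulated trials with arm, baseline and site in the model (95 degrees of freedom). The last column is 100 × (1 − variance ratio).

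**Unequal SDs.** For ρ = 0.5, 0.7, 0.8 and 0.9:

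- k = 0.8: SE lower by 24.4%, 20.8%, 20.0%, 22.0%. Example at ρ = 0.8: 0.64 × 0.36 / (1.64 − 1.28) = 0.64, and √0.64 = 0.80.
- k = 1.2: SE lower by 6.7%, 1.7%, 0.2%, 1.1%.

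**Simulation check.** There were 6,000 trials with sites of 60/20/20, 1:1 within site, no arm effect, and assumed site shifts of 0, +0.5 and −0.5 SD.

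- Unpaired test on change: SE 0.202, 0.156, 0.126, 0.089; type I error 4.7% to 5.4%.
- Arm, baseline and site: SE 0.176, 0.145, 0.121, 0.087; type I error 4.5% to 5.7%. Leaving site out changes the gain by no more than about 0.1 percentage point.
- Skewed scores (exponential of 0.6 × a normal variable, ρ on the log scale): adjustment still lowers the SE by 15%, 9%, 7% and 5%, with type I error of 4.4% to 4.8%.

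A separate simulation with a clean baseline gave mean effects of about zero for both analyses.

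**The paired test read literally.** Take ρ = 0.7 and no difference between arms. The SD of change is √(2 × 0.3) = 0.775. For an assumed drift of 0.1, 0.2 or 0.3 SD common to both arms, the chance p that a given arm of 50 is significant is 0.146, 0.433 or 0.766. The chance that exactly one arm is significant is 2p(1 − p), about 25%, 49% or 36%.

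**If knowledge of the arm affects baseline.** With an assumed 0.2 SD shift of the intervention arm's baseline and no true effect, raw change is biased by 0.20 SD. The adjusted analysis is biased by ρ × 0.2, which is 0.10, 0.14 or 0.18 SD at ρ = 0.5, 0.7 or 0.9. Adjustment reduces this bias but does not remove it.

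**The case against.** The strongest reply is that an unpaired comparison of change is valid, that this is a 100-person feasibility pilot, and that covariates are normally settled in an SAP, which was not available here. Efficacy is a signal listed third among the outcomes. No target interval width is set, and the precision statement does not say which estimates it concerns. If the risk score is stable over two months, the gain may be only 2.5% to 5%, and the 20% to 24% figures need an assumed shrinkage of the SD.

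The paired label also looks like a slip. The alternative test in the same sentence is for independent groups, and the next sentence speaks of a difference between groups. Nothing says that the team would infer an effect from significance in one arm. Baseline timing is a separate bias question: only upper time limits are given, and it is not said when staff or participants learn the allocation.

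Much of this stands, and it limits the point to an improvement rather than a serious flaw. The planned change analysis is not invalid, the gain may be modest, and the order of baseline and disclosure is unspecified rather than shown to be wrong. Two things remain. The protocol is not silent: it names unadjusted tests, one of them mislabelled, and an SAP that added a covariate would not make the label right. Timing also belongs here to this extent: calling either analysis unbiased depends on it.

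**Conclusion.** The point holds, as a matter to consider. The word 'paired' is wrong for a comparison of two independent arms and needs correcting whatever else is decided. The unpaired change analysis is unbiased if baseline precedes disclosure of allocation, but it gives up precision: about 13% to 2.5% in standard error for correlations from 0.5 to 0.9 with equal SDs. The loss is larger if the month-2 SD is smaller than at baseline, and close to nil in some cases if it is larger. The correlation and the SDs are assumptions, so the size is uncertain. The direction is not, apart from the negligible cost in degrees of freedom. The 25%, 49% and 36% figures apply only if the paired test is run literally and read arm by arm. The documents do not show that baseline will be affected by knowledge of the arm; they do not rule it out.

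**What to change.** - Make the main analysis of each score a linear model of the month-2 score on arm, baseline score and site. Report the adjusted mean difference with its 95% CI. Site is included because it is the randomisation stratum, not for its expected gain.
- Keep an unpaired comparison of change as supporting: a t-test, or Mann-Whitney if the change is skewed.
- Delete 'paired', or limit it to describing change within each arm.
- State that baseline scores are obtained before allocation is disclosed to the participant and to the coordinator who takes them.

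The endpoint definitions can stay. The same model fitted to change gives the same arm effect, with the sign reversed for the risk score because the protocol subtracts month 2 from baseline.

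The cost is a change of analysis wording, using data already collected, and three degrees of freedom: one for baseline and two for site, so 98 becomes 95. The one operational step, baseline before disclosure, is needed by the planned change score as well.
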